1. PROTOCOL SUMMARY

1.1. Synopsis

Protocol Title: An open-label, randomized three period cross-over relative bioavailability study to compare the pharmacokinetic parameters of a lower dose formulation of ambrisentan (GSK1325760) with marketed ambrisentan in healthy adult participants

Short Title: Relative bioavailability study of marketed and lower dose ambrisentan in healthy adult participants

Rationale:

Adult treatments are widely used off label for treatment of pulmonary arterial hypertension (PAH) in children; however, conventional drug delivery methods are not always suitable for younger patients who have difficulties with swallowing conventional tablet formulations. Therefore, the aim is to develop an ambrisentan (AMB) tablet for use in children <8 years, which may be dispersed in water or swallowed (dependent on the age or preference of the child), in order to improve patient compliance and acceptability, whilst maintaining safety and efficacy.

The primary objective of this study is to provide clinically relevant information on the pharmacokinetic (PK) and safety profile of a new lower dose formulation AMB tablet, which is intended for paediatric use. The study will compare the relative bioavailability of the lower dose tablet, dispersed in water and administered orally, with the reference marketed AMB tablet in healthy adults. This study is part of a Paediatric Investigational Plan (PIP) agreed with the European Medicines Agency's Paediatric Committee (PDCO).

Objectives and Endpoints:

Objective	Endpoint
Primary	

 To compare the relative bioavailability of AMB (1 mg x 5 tablets) as tablets dispersed in water or administered orally, with marketed AMB (5 mg x 1 tablet) administered orally, in healthy adult participants under fasted conditions. 	
 Plasma pharmacokinetic parameters of AMB, as data permit: C_{max}, t_{max}, $AUC_{(0-\infty)}$, $AUC_{(0-t)}$ and $t_{1/2}$.

Objective	Endpoint
Secondary	

 To monitor the safety and tolerability of AMB (1 mg x 5 tablets) as tablets dispersed in water or administered orally, compared with marketed AMB (5 mg x 1 tablet) administered orally, in healthy adult participants. 	
 Adverse events (AE), vital signs, electrocardiogram (ECG), and clinical laboratory values

Overall Design:

This is a single centre, open-label, randomised, single dose, 3-period cross over study in healthy participants to compare the PK of a new lower dose formulation AMB tablet (dispersed in water and administered orally) with the reference marketed AMB tablet (administered orally).

Disclosure Statement: This is a cross-over relative bioavailability study with 3 arms with no masking.

Number of Participants:

Approximately 24 participants will be randomly assigned to study intervention, such that 20 evaluable participants complete the study.

Intervention Groups and Duration:

Each participant will have 3 treatment periods (single oral doses), and will be randomised to one of the following study interventions in each period:

[figure not shown]
- Test 1 (F1):** 5 mg (5 x 1 mg tablets) AMB tablet dispersed in water
- Test 2 (F2):** 5 mg (5 x 1 mg tablets) AMB tablet administered orally
- Reference (R):** 5 mg (1 x 5 mg tablet) AMB tablet administered orally

Each participant will:

- be screened (within 28 days of their first dose);
- have 3 treatment periods (3 overnight clinic stays, and 1 out-patient visit per treatment period) with a minimum of 7 days between doses in each treatment period; and
- have a follow-up visit (within 7 to 14 days after their last dose). The total study duration for each participant is expected to be approximately 9 weeks.

Data Monitoring Committee: No

1.2. Schema

★ Fasted from midnight prior to dose to 4 hours post dose

1.3. Schedule of Activities (SoA)

1.3.1. Screening and Follow-up Schedule of Activities

Procedure	Screening ¹ (up to 28 days before first dose)	Follow up/Early Withdrawal (7-14 days post last dose)	Notes
Informed consent	X		
Inclusion and exclusion criteria	X		
Demography	X		
Medical history (includes substance usage)	X		Substances: Drugs, Alcohol, tobacco
Full physical exam, including height and weight	X		
Brief physical exam		X	
HIV, Hep B and Hep C screen	X		
Clinical chemistry, haematology and urinalysis	X	X	Only screening tests need to be fasted
FSH	X		Required only in women to confirm postmenopausal status
Alcohol breath test	X		
Urine drugs test	X		
Vital signs (blood pressure, heart rate and temperature)	X	X	Triuplicate blood pressure and heart rate required at screening.
12-lead ECG	X	X	Triuplicate ECG required at screening.
Concomitant Medication review	X	X	Con meds before dosing can be recorded in medical history
AE/SAE review	X	X	Refer to Section 8.3.1

1. Screening assessments may be conducted at multiple visits, if required.

1.3.2. Treatment Periods 1, 2 and 3 (minimum of 7 days washout between doses)

Procedure	Day -1	Day 1 (hours)												Day 2	Day 3	Day 4	Notes
		Pre-dose	0	0.5	1	1.5	2	2.5	4	8	12	18	24	36	48	72	
Clinic Visits																	
Out-patient Visit																X	
Admission to clinic	X																
Discharge from clinic															X		If more convenient for participants, they can remain in the unit until 72 h, at the discretion of the investigator
Study Intervention																	
Randomisation		X															Can be done on Day -1 or Pre-dose Day 1. Only in Treatment Period 1
Study Intervention			X														Fasted from midnight until 4 h post-dose, except for water, allowed ad libitum, except for 1 h before and after dosing
Safety Assessments																	
Vital signs (blood pressure, heart rate and temperature)		X		X	X		X		X	X	X		X		X	X	Triplicate pre-dose. Single measurements at other timepoints, unless out of range, then triplicates should be performed
12-lead ECG		X			X		X		X		X		X			X	
Clinical chemistry, haematology and urinalysis	X														X		Fasting not required
Brief physical examination	X																
Alcohol breath test	X																
Urine drugs test	X																

Procedure	Day -1	Day 1 (hours)												Day 2		Day 3		Day 4	Notes
		Pre-dose	0	0.5	1	1.5	2	2.5	4	8	12	18	24	36	48	72			
Concomitant Medication		←=====→																Con meds before dosing can be recorded in medical history	
SAE/AE review		←=====→																Refer to Section 8.3.1	
Other Assessments																			
PK blood samples			X		X	X	X	X	X	X	X	X	X	X	X	X	X		
Palatability Questionnaire				X														Questionnaire only to be completed in the Treatment Period dosing AMB tablets dispersed in water. To be completed within 10 min of dosing	

- When scheduled at the same time-points, 12-lead ECGs and vital signs should be completed before any blood draws.
- The timing of assessments should allow PK samples to be taken as close as possible to the nominal time-point.
- The timing and number of planned safety assessments and pharmacokinetic samples may be altered during the course of the study based on newly available data (e.g., to obtain data closer to the time of peak plasma concentrations) to ensure appropriate monitoring.
- Any changes in the timing or addition of time points for any planned study assessments as the result of emerging pharmacokinetic data from this study must be documented and approved by the relevant study team member and then archived in the sponsor and site study files but will not constitute a protocol amendment. The Competent Authority (CA) and ethics committee (EC) will be informed of any safety issues that constitute a substantial amendment and require alteration of the safety monitoring scheme or amendment of the informed consent form (ICF). The changes will be approved by the CA and the EC before implementation.

2. INTRODUCTION

Ambrisentan (AMB) (Volibris tablets) is an oral, once daily, propanoic acid-based, Endothelin Receptor Antagonist (ERA), which is selective for Endothelin Receptor Type A. AMB targets the phospholipase-C-dependent endothelin pathway, which is known to play an essential role in mammalian cardiovascular physiology. It is indicated for treatment of pulmonary arterial hypertension (PAH) in adult patients of World Health Organization (WHO) Functional Class (FC) II to III, to improve exercise capacity, decrease the symptoms of PAH, and delay clinical worsening, including use in combination treatment. Efficacy has been shown in idiopathic PAH (IPAH) and in PAH associated with connective tissue disease [[Volibris](#), 2018]. AMB is marketed in the European Union (EU), Japan and over thirty further countries by GlaxoSmithKline (GSK), and in the United States (US) by Gilead Sciences Inc, as Letairis.

2.1. Study Rationale

Adult treatments are widely used off label for treatment of PAH in children; however, conventional drug delivery methods are not always suitable for younger patients who have difficulties with swallowing conventional tablet formulations. Therefore, the aim is to develop an AMB tablet for use in children <8 years, which may be dispersed in water or swallowed (dependent on the age or preference of the child), in order to improve patient compliance and acceptability, whilst maintaining safety and efficacy.

The primary objective of this study is to provide clinically relevant information on the PK and safety profile of a new lower dose formulation AMB tablet, which is intended for paediatric use. The study will compare the relative bioavailability of the lower dose tablet, dispersed in water and administered orally, with the reference marketed AMB tablet in healthy adults. This study is part of a Paediatric Investigation Plan (PIP) agreed with the European Medicines Agency's Paediatric Committee (PDCO).

An exploratory objective of this study is to assess the palatability of the new lower dose formulation AMB tablet dispersed in water.

2.2. Background

PAH is a rare, progressive, highly debilitating and life-threatening disease characterized by pulmonary vascular functional and structural changes resulting in increased pulmonary vascular resistance (PVR) and eventual right-sided heart failure (RHF) and premature death [[Moledina](#), 2010; [Newman](#), 2004; [Vorhies](#), 2014].

Epidemiological data estimates PAH incidence in Europe ranges from 1.1 to 7.6 per million; prevalence ranges from 6.6 to 26 per million [[Hoepel](#), 2016]. Large scale epidemiology studies of PAH in children have not been conducted and there is no or limited outcome data in paediatric PAH patients. A register in France (1995–1996) estimates the prevalence in children is as low as 3.7 cases per million [[Fraisne](#), 2010]. In a national, comprehensive country wide survey of the epidemiology of IPAH management and survival in the UK, the incidence was 0.48 cases per million children per year, and the prevalence was 2.1 cases per million children [[Moledina](#), 2010].

Despite the emergence of new treatments, PAH still has a poor long-term prognosis (akin to many cancers). A recent meta-analysis estimates survival for untreated IPAH in adults to be only 79% at 1 year and 66% at 2 years [McLaughlin, 2006]. In the UK, survival in treated children with IPAH at 1, 3 and 5 years was 89%, 84%, and 75% respectively; whilst transplant free survival was 89%, 76%, and 57%, respectively [Moledina, 2010].

The pathophysiologic mechanisms which underpin the disease spectrum of PAH involve pulmonary vascular dysfunction, which produces an imbalance in vasoactive substances, as well as proliferation signals that lead to structural remodeling and pulmonary vasoconstriction. Although its role is not fully understood, endothelin is considered an important mediator of pathology in PAH. Almost all components of the endothelin system are upregulated in PAH [Giaid, 1993; Galiè, 2004]. There appears to be a significant correlation between serum endothelin 1 levels and disease severity, reflected by elevations in PVR, mean pulmonary artery pressure (mPAP) and right atrial pressure [Nootens, 1995]. Endothelin-1 (ET-1) receptor antagonists are a targeted pharmacological approach that limit both the vasoconstrictor and proliferative action of endothelin [Dingemanse, 2004], and in this way ameliorate the clinical manifestations of the disease.

Treatments currently approved for the treatment of PAH target 3 biological pathways: endothelin, nitric oxide, and prostacyclin pathways. There is evidence that prostanoid therapies are effective in children, but in common to their use in adults, the pharmacokinetic properties of these drugs and routes of administration (e.g., intravenous, subcutaneous injection, or multiple inhalations) present substantial challenges to their successful use in a pediatric population.

The efficacy profile of AMB in adults is broadly comparable with other targeted oral treatments, but it has potentially important advantages. AMB is associated with a favourable liver safety profile and a low risk of drug-drug interactions. Data from the TRAX¹ database indicates that the risk of elevated aminotransferases with bosentan (another marketed ERA) is lower in children than adults [Beghetti, 2008]. Nevertheless, the liver safety profile of AMB in adults has been favorable to bosentan, and if replicated in children, would provide a clinically useful option. Children, like adults with PAH, commonly require many concomitant medications. The low risk of drug-drug interactions and convenient once a day dosing associated with AMB, may provide a therapeutic option that simplifies treatment in this complex disease.

A detailed description of the pharmacology, efficacy, and safety of AMB is provided in the Volibris European Medicines Agency (EMA) Summary of Product Characteristics [SmPC, 2018].

¹ TRAX - the Tracleer Excellence database is a non-interventional, prospective, internet-based surveillance system initiated by the manufacturer in cooperation with Regulatory agencies to collect potential safety signals associated with bosentan use, including: adverse events, elevations of liver aminotransferase levels, other abnormal laboratory values, deaths, and hospitalization [Segal, 2005].

2.3. Benefit/Risk Assessment

More detailed information about the known and expected benefits and risks and reasonably expected adverse events of AMB (GSK1325760) may be found in the Volibris EMA Summary of Product Characteristics [[SmPC](#), 2018].

2.3.1. Risk Assessment

Potential Risk of Clinical Significance	Summary of Data/Rationale for Risk	Mitigation Strategy
Investigational Product (IP) AMB (GSK1325760)		

Identified and potential risks, from European Union Risk Management Plan (EURMP) for Volibris:
 
 • Teratogenicity • Decreased haemoglobin/haematocrit, anaemia, including anaemia requiring transfusion • Hepatotoxicity • Testicular tubular atrophy/Male infertility 
Consistent with the mechanism of action for AMB, there is a potential risk of hypotension in healthy participants.
	
 • Refer to EURMP for Volibris v8.1 (EURMP, 2019) • Refer to Volibris EMA Summary of Product Characteristics (SmPC, 2018) 	
Exclusion criteria, ongoing safety assessments, study design and medical supervision. Specifically:
 
 • The use of single doses in this study. • Exclusion of women of child bearing potential. • Exclusion of potentially anaemic participants. • Haemoglobin reduction withdrawal criterion for individual participants. • Inclusion criteria to prevent enrolment of hypotensive participants. • Hypotension withdrawal criterion for individual participants. • Laboratory assessments per protocol. • Physical assessment per protocol. • Routine vital signs per protocol. • Participants remain in the clinical unit, under medical supervision, for all doses and until completion of safety assessments at 48 hrs post dose.
Study Procedures		
Risk associated with blood draws	Fainting, mild pain, bruising, irritation or redness at phlebotomy site, may be associated with blood draws.	Experienced site staff will follow standard approaches for managing events related to blood draws.

2.3.2. Benefit Assessment

There is no clinical benefit for healthy participants taking part in this study. However, participants will undergo a medical evaluation during screening (including a physical examination, electrocardiogram (ECG), vital signs and laboratory assessments), which may provide important health information.

2.3.3. Overall Benefit: Risk Conclusion

Taking into account the measures taken to minimize risk to participants participating in this study, the potential risks identified in association with AMB are justified by the anticipated benefits that may be afforded to paediatric patients with PAH.

3. OBJECTIVES AND ENDPOINTS

Objective	Endpoint
Primary	

 To compare the relative bioavailability of AMB (1 mg x 5 tablets) administered as tablets dispersed in water or administered orally, with marketed AMB (5 mg x 1 tablet) administered orally, in healthy adult participants under fasted conditions. 	
 Plasma pharmacokinetic parameters of AMB, as data permit: C_{max}, t_{max}, $AUC_{(0-\infty)}$, $AUC_{(0-t)}$ and $t_{1/2}$.
Secondary	

 To monitor the safety and tolerability of AMB (1 mg x 5 tablets) administered as tablets dispersed in water or administered orally, compared with marketed AMB (5 mg x 1 tablet) administered orally, in healthy adult participants. 	
 Adverse events (AE), vital signs, electrocardiogram (ECG), and clinical laboratory values.
Exploratory	

 To investigate palatability of AMB (1 mg x 5 tablets) dispersed in water, in healthy adult participants. 	
 Palatability questionnaire scores

4. STUDY DESIGN

4.1. Overall Design

This is a single centre, open-label, randomised, single dose, 3-period cross over study in healthy participants to compare the PK of a new lower dose formulation AMB tablet

(dispersed in water and administered orally) with the reference marketed AMB tablet (administered orally). Each participant will have 3 treatment periods (single oral doses), and be randomised to one of the following study interventions in each period:

- **Test 1 (F1):** 5 mg (5 x 1 mg tablets) AMB tablet dispersed in water
- **Test 2 (F2):** 5 mg (5 x 1 mg tablets) AMB tablet administered orally
- **Reference (R):** 5 mg (1 x 5 mg tablet) AMB tablet administered orally

Each participant will:

- be screened (within 28 days of their first dose);
- have 3 treatment periods (3 overnight clinic stays, and 1 out-patient visit per treatment period), with a minimum of 7 days between doses in each treatment period; and
- have a follow-up visit (within 7 to 14 days after their last dose).

The total study duration for each participant is expected to be approximately 9 weeks.

4.2. Scientific Rationale for Study Design

This open-label, randomized, cross-over design is well-established for the evaluation of relative bioavailability of different oral dosage forms. Randomization of the treatment sequences is an attempt to prevent bias. No blinding or placebo control will be used, as these are not required for the primary study objective (PK assessment). The washout of 7 days between doses should eliminate the possibility of carryover of drug exposure from the previous dosing period, because AMB $t_{1/2}$ is 17 h.

4.3. Justification for Dose

The approved doses of AMB for the treatment of adult PAH patients are 5 mg and 10 mg, once daily [SmPC, 2018]. AMB is not approved for the treatment of paediatric PAH patients. An alternate tablet that may be dispersed in water or swallowed is therefore in development for paediatric patients <8 years old, who may have difficulty swallowing tablet formulations. The 5 mg AMB tablet has been studied in paediatric patients (8 to 18 years old) in GSK Study AMB112529 [Volibris, 2018].

The current study will compare the relative bioavailability of 5 x 1 mg tablets dispersed in water (administered as ‘disperse in water and immediately take’) and 5 x 1 mg tablets (administered orally), with that of 1 x 5 mg marketed tablet (reference) (administered orally).

Using the 5 mg AMB tablet as the reference dose allows assessment of the relative bioavailability comparison with the lower dose tablet but requires participants to take only 5 x 1 mg tablets – rather than 10 tablets (which would have been required if the 10 mg AMB tablet had been selected as the reference). This decreases the participant burden for the study. The reference 5 mg AMB tablet is quantitatively proportional to the 10 mg AMB tablet, and so, 2 x 5 mg tablets are equivalent to 1 x 10 mg tablet (Studies EE-001, EE-002 and AMB-103) [Volibris, 2018].

4.4. End of Study Definition

A participant is considered to have completed the study if he/she has completed all phases of the study including the follow-up visit.

The end of the study is defined as the date of the last visit of the last participant in the study.

5. STUDY POPULATION

Prospective approval of protocol deviations to recruitment and enrolment criteria, also known as protocol waivers or exemptions, is not permitted.

5.1. Inclusion Criteria

Participants are eligible to be included in the study only if all of the following criteria apply:

Age
1. Participant must be 18 to 65 years of age inclusive, at the time of signing the informed consent.

Type of Participant and Disease Characteristics
2. Participants who are overtly healthy as determined by medical evaluation including medical history, physical examination, laboratory tests, vital signs and cardiac monitoring (refer to Section 5.4 for information about rescreening). 3. Average systolic blood pressure between 100-160 mmHg and diastolic between 55-90 mmHg (inclusive) over 3 readings at screening.

Weight
4. Body weight \geq 50 kg for men and \geq 45kg for women, and body mass index (BMI) within the range 18-30 kg/m ² (inclusive).

Sex
5. Male or female a. Male participants: Male participants are eligible to participate if they agree to the following during the study and for at least 13 weeks afterwards corresponding to time needed to eliminate study intervention (5 terminal half-lives) plus an additional 90 days (a spermatogenesis cycle):

- Refrain from donating sperm

PLUS either:

- Be abstinent from heterosexual intercourse as their preferred and usual lifestyle (abstinent on a long term and persistent basis) and agree to remain abstinent

OR

- Must agree to use contraception/barrier, as follows:
 - Agree to use a male condom; and
 - Female partner to use an additional highly effective contraceptive method with a failure rate of <1% per year as described in [Appendix 4](#).

b. Female participants:

A female participant is eligible to participate if she is not a woman of childbearing potential (WOCBP), as defined in [Appendix 4](#).

Informed Consent

6. Capable of giving signed informed consent as described in [Appendix 1](#) which includes compliance with the requirements and restrictions listed in the informed consent form (ICF) and in this protocol.

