7. DISCONTINUATION OF STUDY INTERVENTION AND PARTICIPANT DISCONTINUATION/WITHDRAWAL

7.1. Discontinuation of Study Intervention

In rare instances, it may be necessary for a participant to permanently discontinue study intervention. If study intervention is permanently discontinued, the participant will not remain in the study. The participant will remain at the clinic until the investigator or delegate discharges the participant. An early withdrawal visit should be conducted (see SOA).

[figure not shown]

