7.2. Participant Discontinuation/Withdrawal from the Study

- A participant may withdraw from the study at any time at his/her own request, or may be withdrawn at any time at the discretion of the investigator for safety, behavioural, compliance or administrative reasons. This is expected to be uncommon.
- At the time of discontinuing from the study, if possible, an early discontinuation visit should be conducted, as shown in the SoA. See SoA for data to be collected at the time of study discontinuation and follow-up.
- The participant will be permanently discontinued both from the study intervention and from the study at that time.
- If the participant withdraws consent for disclosure of future information, the sponsor may retain and continue to use any data collected before such a withdrawal of consent.
- If a participant withdraws from the study, he/she may request destruction of any samples taken and not tested, and the investigator must document this in the site study records.

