7.3. Lost to Follow Up

A participant will be considered lost to follow-up if he or she repeatedly fails to return for scheduled visits and is unable to be contacted by the study site.

The following actions must be taken if a participant fails to return to the clinic for a required study visit:

- The site must attempt to contact the participant and reschedule the missed visit as soon as possible and counsel the participant on the importance of maintaining the assigned visit schedule and ascertain whether or not the participant wishes to and/or should continue in the study.
- Before a participant is deemed lost to follow up, the investigator or designee must make every effort to regain contact with the participant (where possible, 3 telephone calls and, if necessary, a certified letter to the participant's last known mailing address or local equivalent methods). These contact attempts should be documented in the participant's medical record.
- Should the participant continue to be unreachable, he/she will be considered to have withdrawn from the study.

Information regarding discontinuation of the study as a whole is given in [Appendix 1](#).

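### Criterion 5a's minimum of 13 weeks (91 days) is 2.5 days below the sum it is said to represent (93.5 days), though men who attend the follow-up visit are covered for 98 to 105 days

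*Protocol*

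**What the plan says.** Protocol Section 5.1, criterion 5a, sets the male commitment. It applies during the study and then "for at least 13 weeks afterwards corresponding to time needed to eliminate study intervention (5 terminal half-lives) plus an additional 90 days". The 90 days are explained as one spermatogenesis cycle.

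The only half-life in the protocol is in Section 4.2, where the 7-day washout is judged sufficient "because AMB $t_{1/2}$ is 17 h".

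Three other places determine what the commitment amounts to:

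- Section 4.4 treats a participant as having completed the study once all phases, including the follow-up visit, are done. It separately defines the end of the study as the last participant's last visit.
- Section 1.3.1 schedules that visit as "Follow up/Early Withdrawal (7-14 days post last dose").
- On early departures, Section 7.1 says "An early withdrawal visit should be conducted (see SOA"), Section 7.2 asks that "if possible, an early discontinuation visit should be conducted, as shown in the SoA", and Section 7.3 ends its list of contact attempts with "Should the participant continue to be unreachable, he/she will be considered to have withdrawn from the study".

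**The concern.** The criterion gives both a figure and the sum behind it, and the two do not agree. The sum comes to more than 13 weeks, yet 13 weeks is set as a floor. A floor derived this way should be rounded up, and this one appears to have been rounded down.

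The clause is an operative eligibility commitment, and Section 5 allows no waivers. The first entry in the list of identified and potential risks in Section 2.3.1 is "Teratogenicity". Under Section 8.3.5, partner pregnancies are collected only until the follow-up visit, so after that visit compliance rests on the man following the stated period. The figure should therefore match its rationale. At stake is a few days of cover for an unusual participant. No estimate, interval or analysis in the trial depends on it.

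**Working it through.** **Inputs.** Stated minimum: 13 weeks (Section 5.1). Stated basis: 5 terminal half-lives plus 90 days (Section 5.1). Half-life: 17 h (Section 4.2). Follow-up or early-withdrawal visit: 7 to 14 days after the last dose (Section 1.3.1). Planned discharge at 48 h and out-patient visit at 72 h (Section 1.3.2).

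**The plan's figure.** 13 × 7 = 91 days.

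**The stated basis.**

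- 5 × 17 h = 85 h; 85 / 24 = 3.54 days.
- 3.54 + 90 = 93.54 days; 93.54 / 7 = 13.36 weeks.
- Difference: 93.54 − 91 = 2.54 days, or 61 h.

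The 13 weeks are reproduced only by rounding 13.36 to the nearest whole week. After the 90-day cycle, 91 days leaves 24 h for elimination, and 24 / 17 = 1.4 half-lives instead of 5. The stated sum would equal 91 days only with a half-life of (91 − 90) × 24 / 5 = 4.8 h.

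**What the criterion delivers.** The 13 weeks start after the study. Let t be the time from a man's last dose to the end of his participation. His cover after the last dose is 91 days + t.

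| t | Cover (days) | Against 93.54 days |
|---|---|---|
| 0 (leaves at dosing) | 91 | 2.54 short |
| 24 h | 92 | 1.54 short |
| 48 h (planned discharge) | 93 | 0.54 short (13 h) |
| 61 h | 93.54 | equal |
| 72 h (out-patient visit) | 94 | 0.46 spare |
| 7 days | 98 | 4.46 spare |
| 14 days | 105 | 11.46 spare |

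**The other meaning of the end of the study.** If the 13 weeks start at the last participant's last visit (Section 4.4), t runs to that date for every man. Cover for visit attenders is then at least the 98 to 105 days above and usually longer. A man who leaves early without a visit also has no shortfall, unless no one else has a visit more than about 61 h after his last dose.

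**The case against.** The strongest reply is that the criterion does have a start point, the end of the study. The 2.5-day figure compares the derivation with 91 days from the last dose, which is not the commitment the text sets. On the text as written, a man who completes the study exceeds the derivation by 4.5 to 11.5 days. This stands. A reader might infer that all men are left 2.5 days short, or that the start of the period is undefined. The documents support neither: the criterion counts from after the study, and Section 4.4 says when that is, for a participant and for the trial.

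The exposed case is also remote. Section 2.3.1 states: "Participants remain in the clinical unit, under medical supervision, for all doses and until completion of safety assessments at 48 hrs post dose". An early-withdrawal visit is expected after permanent discontinuation, and a man is treated as lost only after repeated missed visits and contact attempts. This stands too, although Section 7.2 makes the visit conditional, so the case is not excluded.

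It can further be said that 13.36 rounds to 13 and that the clause offers a rationale, not an equation. This carries less weight, because the figure is a minimum and nothing in the text says that follow-up time makes up the difference.

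Finally, the mitigation in Section 2.3.1 that bears directly on teratogenicity is the exclusion of women of childbearing potential. The protocol states no male-mediated risk, and dosing is three single doses. So nothing here shows that 2.5 days would alter risk, and the point does not claim it.

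**Conclusion.** The stated minimum is wrong against its own basis: 91 days against 93.5, a difference of 2.5 days (2.7% of the sum). This rests on the 17 h half-life, the only one the protocol gives; any half-life above 4.8 h leaves 91 days below the sum.

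The effect on participants is very small. Men who attend the visit at 7 to 14 days have no shortfall on either meaning of the end of the study. A shortfall needs one of two things. The first is that participation ends within about 61 h of a dose with no later visit, with the period counted from that man's own departure. The gap is then 13 h at the planned 48 h discharge, and at most 2.5 days if he leaves at dosing. The second is that a site departs from the wording and counts from the last dose, which gives the full 2.5 days.

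The point is minor. It concerns a figure in a binding safety commitment. It does not show inadequate protection of participants' partners, and it touches no endpoint, sample size or analysis.

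**What to change.** In criterion 5a, change 13 weeks to 14 weeks and leave the start point as it is, after the end of the study. Cover becomes 98 days + t. The smallest margin over the derivation is 98 − 93.54 = 4.46 days, for a man who leaves at dosing or at a site that counts from the last dose. Visit attenders would be covered for 105 to 112 days. No one's commitment is reduced. The cost is one changed figure and 7 more days in each man's minimum, although those who attend the visit already exceed the derivation.

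An acceptable alternative is to require 14 weeks (98 days) counted from the last dose. It gives the same 4.46-day margin for every man, whatever his attendance, and names the start point directly. Its change from the present commitment is 7 − t days: 7 more for a man who leaves at dosing, 5 more at the 48 h discharge, 4 more at 72 h, none at day 7, and 7 fewer at day 14. It therefore shortens the commitment for men seen after day 7, which is why the first change is preferred.
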